(a) Routine blood test: white blood cell, neutrophil, lymphocyte, neutrophil ratio, lymphocyte ratio, red blood cell, hemoglobin, platelet.

(b) Blood biochemistry: alanine aminotransferase, aspartate aminotransferase, alkaline phosphatase, lactate dehydrogenase, gamma glutamyltransferase, total bilirubin, direct bilirubin, total protein, albumin, urea, creatinine, uric acid, glucose, triglyceride, total cholesterol, potassium, sodium, chloride, calcium, phosphorus.

(c) Routine blood coagulation: prothrombin time, activated partial thromboplastin time, thrombin time, fibrinogen, prothrombin time -INR.

(8) Auxiliary examinations:

(a) Auxiliary examinations in the screening period include: BCVA OU, IOP OU, OCT of study eye, wide angle CP of study eye, the multifocal electroretinogram of study eye, microperimetry analysis of study eye, ocular axis measurement of study eye, B-scan ultrasound of study eye. Accept the examination results carried out before the informed consent signature during the same hospitalization.

(b) Auxiliary examinations in V1 and 2 include: BCVA OU, IOP OU, OCT of study eye, wide angle CP of study eye; ocular axial measurement of study eye;

(c) Auxiliary examinations in V3 include: BCVA OU, IOP OU, OCT of study eye, wide angle CP of study eye, B-scan ultrasound of study eye;

(d) Auxiliary examinations in V4 include: BCVA OU, IOP OU, OCT of study eye, wide angle CP of study eye;

(e) Auxiliary examinations in V5, 6, 7, end visits, and unscheduled visits include: BCVA OU, IOP OU, OCT of study eye, wide angle CP of study eye, the multifocal electroretinogram of study eye, microperimetry analysis of study eye and B-scan ultrasound of study eye .

(9) The low vision quality of life questionnaire: Subjects were asked to self-rate according to the low vision quality of life questionnaire (Attachment 3);

(10) Adverse events: Adverse events were collected from the time the subjects sign informed consent until the end of the study.

(11) Previous/ combined medication: Collect relevant information from the time the subjects sign informed consent until the end of the study, including all the medication used for the treatment of AE or SAE.

9. Outcome Assessment

1) Primary Outcome Assessment:

Macular hole closure rate: Fundus examination combined with optical coherence tomography (OCT) are performed 3 months after surgery.

2) Secondary Outcome Assessment:

Best corrected visual acuity (LogMAR): 6 months after the surgery

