Reattachment rate of retinal detachment: Use fundus examination combined with B-scan ultrasound, optical coherence tomography (OCT) to observe the reattachment rate of retinal detachment within 12 months after the surgery.(The reattachment rate assessment is performed 12 months after the first surgery among the patients with air tamponade. The reattachment rate assessment is performed 12 months after the first surgery among the patients with silicone oil tamponade, and the silicone oil removal is performed 6 months after the previous surgery.)

Postoperative complication rate

10. Adverse event

(1) Adverse events (AE) refer to any adverse event that occurs during clinical studies, but do not necessarily have causal relationship with the surgery.

Safety evaluation should be carried out from the signature of the informed consent until the end of the study, according to management requirements (Adverse events or serious adverse events should be reported).

(2) Severe adverse events (SAE) refer to the occurrence of hospitalization, prolonged

hospitalization, disability, incapacity, life-threatening or death, congenital malformations during the clinical trials.

(3) Record of adverse events

During the study, all adverse events should be recorded. Records should include the name of AE (using the standard medical terminology), the date of AE occurrence and disappearance / stabilization, severity, impact on the surgery, relationship with the surgery, treatment measures and outcomes.

(4) Reports of serious adverse events

If serious adverse events occur, researchers must fill in the report of serious adverse events. The report should be signed and dated, and be reported to the ethics committee within 24 hours.

11. Target case load and sample size calculation

Target case load: 38

The study uses the superiority design. According to the references and the professional judgment, macular hole closure rate is 25% in the control group (group 1), while in the experimental group (group 2), macular hole closure rate is 65%. The significant level α is 0.05, and test performance (1- beta) is 0.80. The software of NCSS PASS 14 is used, and each group has 17 cases with the loss rate of 10%. The final sample size is 38.

12. Randomization

Stratified randomization is conducted according to the extent of retinal detachment [type 1 (within the arcade area), type 2 (beyond the arcade area)]. The software of NCSS PASS 14 will be used. The study includes 2 groups.

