13. Masking method

In this study, the third party independent evaluation method is used to evaluate the results of the study. The analyzer is in the masking state, and the patients and the surgeons are in the non-masking state.

14. Statistical data processing

(1) Validity analysis: Descriptive statistical method is used to describe the research indicators. Univariate analysis of continuous variables is performed using ANOVA, and univariate analysis of categorical variables is performed using chi square test. The repeated measurement data are

analyzed by mixed effect model. The population of effectiveness analysis is the population of people with intention to be treated.

(2) Safety analysis: The safety assessment of clinical parameters (including adverse events, laboratory tests, vital signs, etc.) will be carried out. Descriptive statistics method is adopted. The safety analysis of the population is the population of all groups received treatment.

(3) Subgroup analysis: To determine whether the therapeutic effects of different subgroups are consistent, the component outcomes (and 95% confidence interval (CI)) are estimated for the major endpoints within the subgroup of the following categorical variables:

The type of retinal detachment [type 1 (within the arcade area), type 2 (beyond the arcade area)]
Gender (male and female)

15. Study implementation period (Anticipated)

April 7th, 2017 to April 6th, 2020

16. Quality Control

The researcher and laboratory personnel involved in this project must have the professional knowledge and experience required in the study protocol;

The researchers and other staff involved in the study perform their duties, and strictly follow the clinical trial plan and adopt standard operating procedures to ensure the implementation of the quality control and quality assurance system;

To ensure that the data is complete, accurate, authentic and reliable, all the relevant observation results and findings need to be verified in each phase of the clinical trials;

The researchers and other staff who participated in the study have sufficient time and reliable sources of subjects for the study;

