Axial length ≥ 26 mm, or the refractive error ≥ -6.0 D

Key exclusion criteria

Exclusion criteria for general medical history:

Local or systemic surgical contraindications at screening or baseline

For both eyes:

With any ocular eye or periocular infection or inflammation (e.g., blepharitis, conjunctivitis, keratitis, scleritis, uveitis, endophthalmitis) at screening or baseline;

With uncontrolled glaucoma at screening or baseline (IOP ≥ 30 mmHg when receiving medical treatment or as judged by the researchers);

With the presence of iris neovascularization or neovascular glaucoma at screening or baseline.

For research eye:

With ocular diseases which may interfere the study results at screening or baseline , including severe vitreous hemorrhage, peripheral retinal hole, proliferative diabetic retinopathy, proliferative vitreoretinopathy (\geq Level C), choroidal detachment;

With other causes which may result in macular hole associated-retinal detachment at screening or baseline, except high myopia;

Previously underwent scleral buckling surgery.

Exclusion criteria for past or current systemic drug use:

With current or planned medication known to have toxic effects on the lens, retina or optic nerve, including hydroxychloroquine, chloroquine, hydroxychloroquine, tamoxifen, phenothiazine and ethambutol.

Study design

This study is a prospective, randomized, controlled study, involving multiple visits within 12 months. The patients with macular hole retinal detachment secondary to high myopia are randomly

divided into 2 treatment groups:

Group 1: The patients in Group 1 are treated by the surgical method of standard 3-port 23 gauge pars plana vitrectomy + internal limiting membrane peeling + air-fluid exchange + silicone oil infusion

Group 2: The patients in Group 2 are treated by the surgical method of standard 3-port 23 gauge pars plana vitrectomy + internal limiting membrane peeling + inverted internal limiting membrane insertion + air-fluid exchange

Sample size calculation

The study uses the superiority design. According to the references and the professional judgment, macular hole closure rate is 25% in the control group (group 1), while in the experimental group (group 2), macular hole closure rate is 65%. The significant level α is 0.05, and test performance (1- beta) is 0.80. The software of NCSS PASS 14 is used, and each group has 17 cases with the loss rate of 10%. The final sample size is 38.

Grouping method

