Patients are assessed whether they meet the inclusion/exclusion criteria before inclusion. The clinical research center completes the compliance assessment form, preoperative consents and informed consent. Informed consent is a qualified standard, since it is agreed by the subjects to be selected, randomly assigned, and agreed to complete the regular follow-up after the surgery.

1) Informed consent of the subjects

In this study, researchers must explain the research purpose, process, possible profit and risk to the subjects (or the legal representative, or witnesses). Only when the subjects (or the legal representative, or witnesses) fully understand the study, and sign informed consent, can they be selected.

The informed consent form should be signed by the subjects (or their legal representatives or witnesses) and the researcher who executed the informed consent procedure in two copies, each of which has one copy.

2) Allocation of screening number of subjects

The subjects who signed the informed consent will be assigned to a screening number. The center will assign a number of 4 Arabia numbers to each subject, with individual uniqueness. Among them, the first number represents the clinical center number, and the second, third, fourth number is the ordinal number, which is assigned to each subject according to the chronological order of the informed consent agreement. The subjects name writing rules: When the name is consisted with two characters, fill in the first two letters of each phonetic alphabet; When the name is consisted with three characters, fill in the first letters of each phonetic alphabet and the second letter of the third phonetic alphabet; When the name is consisted with four characters, fill in the first letters of each phonetic alphabet; When the name is consisted with five or more than five characters, fill in the first letters of the first four phonetic alphabets.

Randomized controlled clinical trial design is used in this study.

Randomization: Stratified randomization is conducted according to the type of retinal detachment [type 1 (within the arcade area), type 2 (beyond the arcade area)]. The software of NCSS PASS 14 will be used. The study includes 2 treatment groups.

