According to randomization procedures, the researchers assign ID numbers to patients. The ID number of the randomization group must be recorded together with the patient screening number in a random directory. Completed random directory should be signed and hand over to the data center by the researcher.

Masking method

In this study, the third party independent evaluation method is used to evaluate the results of the study. The analyzer is in the masking state, and the subjects and the surgeons are in the non-masking state.

Outcome evaluation

1) Primary Outcome Measures:

To evaluate the effectiveness of different surgical procedures by evaluating the following

indicators:

The difference between macular hole closure rate, closed type in each group from baseline to the 3rd month

2) Secondary Outcome Measures:

To evaluate the effectiveness and safety of different surgical procedures by evaluating the following indicators:

The difference of the reattachment rate of retinal detachment between each group from baseline to the 6th month

The difference of the reattachment rate of retinal detachment between each group from baseline to the 12th month

The change of BCVA relative to baseline and the difference between groups from baseline to the 6th month

The change of BCVA relative to baseline and the difference between groups from baseline to the 12th month

The number of people whose BCVA result improves by more than 1 row, 2 rows and 3 rows comparing to the baseline at a time.

The number of people whose BCVA result decreases by 3 rows comparing to the baseline at a time

The difference of multifocal ERG results between each group from 1 week to the 6th month after surgery

The difference of multifocal ERG results between each group from 1 week to the 12th month after surgery

The change of microperimetry analysis results from 1 week to the 6th month after surgery relative to baseline, and the difference between each group

The change of microperimetry analysis results from 1 week to the 12th month after surgery relative to baseline, and the difference between each group

The change of the extent of foveal ellipsoid zone damage from baseline to the 6th month after the surgery relative to baseline, and the difference between each group

The change of the external limiting membrane integrity of fovea from baseline to the 6th month after the surgery relative to baseline, and the difference between each group

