The change of the extent of foveal ellipsoid zone damage from baseline to the 12th month after the surgery relative to baseline, and the difference between each group

The change of the external limiting membrane integrity of fovea from baseline to the 12th month after the surgery relative to baseline, and the difference between each group

Describe the number of retreatment and retreatment modalities for patients with different surgical procedures over a period of 12 months

Evaluate the safety of different surgical procedures by assessing the type, frequency and severity of ocular adverse events and non-ocular adverse events or severe adverse events during 12 months

Data analysis

(1) Validity analysis: Descriptive statistical method is used to describe the research indicators. Univariate analysis of continuous variables is performed using ANOVA, and univariate analysis of categorical variables is performed using chi square test. The repeated measurement data are analyzed by mixed effect model. The population of effectiveness analysis is the population of people with intention to be treated.

(2) Safety analysis: The safety assessment of clinical parameters (including adverse events, laboratory tests, vital signs, etc.) will be carried out. Descriptive statistics method is adopted. The safety analysis of the population is the population of all groups received treatment.

(3) Subgroup analysis: To determine whether the therapeutic effects of different subgroups are consistent, the component outcomes (and 95% confidence interval (CI)) are estimated for the major endpoints within the subgroup of the following categorical variables:

The type of retinal detachment [type 1 (within the arcade area), type 2 (beyond the arcade area)]

Gender (male and female)

CRC assistance

The study requires one to two clinical research coordinator (CRC)

Responsibilities:

-
- (1) Contact the subjects before 3-7 days before a follow-up;
 - (2) Communicate with the director in advance, and make appointments for patient follow-ups;
 - (3) Arrange the relevant examination for the patients;
 - (4) Have good communication skills;
 - (5) Fill in Case Report Form.

Benefit status of subjects

The therapy in this study may help to further control the patient's condition, to optimize the treatment of the disease, to provide the necessary advice for the future treatment of patients, to provide useful information for treatment or disease;

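### Randomisation is stratified by detachment type, but the only test named for 3-month closure is an unstratified chi-square: a valid test that turns conservative if type is prognostic

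*Protocol*

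**What the plan says.** **Randomisation.** Protocol summary, section 12: "Stratified randomization is conducted according to the extent of retinal detachment". The detailed protocol, under Grouping method, repeats it: "Stratified randomization is conducted according to the type of retinal detachment". Both define type 1 as within the arcade area and type 2 as beyond it.

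**Primary endpoint.** Section 9: "Macular hole closure rate: Fundus examination combined with optical coherence tomography (OCT) are performed 3 months after surgery". This is one binary outcome per patient at one time point.

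**Analysis.** Section 14 (1): "Univariate analysis of continuous variables is performed using ANOVA, and univariate analysis of categorical variables is performed using chi square test". The detailed Data analysis section has the same sentence. Repeated measurements go to a mixed effect model, which does not cover a single binary outcome.

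**Other use of the stratum.** Detachment type returns only in the subgroup analysis, as within-subgroup estimates with 95% CIs. Neither section names a between-group test or risk difference that takes account of type.

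**The concern.** Stratifying on a factor treats it as possibly prognostic. If it is, balancing the arms on it removes part of the chance variation in the difference between arms. A plain chi-square still allows for that variation, so its standard error is too large and it rejects less often than its nominal level. With 38 patients, a few points of power are worth having when the stratum is already known for everyone.

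At stake are the power of the primary test and the match between the design and the reported risk difference. The credibility of a positive result is not at stake, because the error is on the conservative side.

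**Working it through.** **Inputs from the protocol.** Closure 25% in group 1 and 65% in group 2; alpha 0.05 with sidedness not stated; power 0.80; "each group has 17 cases with the loss rate of 10"%; 38 in total (section 11 and Sample size calculation).

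**The plan's own figure.** A one-sided 5% z-test with unpooled variance gives
n = (1.645 + 0.842)² × (0.25×0.75 + 0.65×0.35) / 0.40² = 16.04, so 17 per group. Then 17/0.9 = 18.9, so 19 per group and 38 in total. The figure reproduces.

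**Assumptions not in the protocol.** Two-sided 5%; the closure gap d between types, taken as 0 to 40 points; the mix of types; arms balanced within strata; the same gap in both arms.

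**Stratum rates.** With share w in the better type and average rate p, the better type has p + (1 − w)d and the other p − wd. Example: 10 and 9 per arm, d = 0.40, controls: 0.25 + (9/19)(0.40) = 0.439 and 0.25 − (10/19)(0.40) = 0.039. The 40-point case therefore means about 44% against 4% closure in controls, which is an upper end.

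**Tests.** Pearson: z = (p2 − p1) / √[p(1 − p)(1/n1 + 1/n2)], with p the pooled rate. CMH, uncorrected: z = Σ(b − s·k/M) / √Σ[m·k·s(M − s) / (M²(M − 1))]. Within each stratum, m and k are the two arm sizes, M their sum, s the total closures and b the closures in group 2. Every possible 2×2×2 table was enumerated, so the balanced-strata power and size are exact.

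**Power, equal strata, in %** (changes from unrounded values):

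| Gap (points) | 19/arm (10/9): chi-square | CMH | Change | 17/arm (9/8): chi-square | CMH | Change |
|---|---|---|---|---|---|---|
| 0 | 72.9 | 70.6 | -2.3 | 69.4 | 69.5 | +0.1 |
| 10 | 73.0 | 71.6 | -1.4 | 69.5 | 69.7 | +0.1 |
| 20 | 73.2 | 74.3 | +1.0 | 69.8 | 70.4 | +0.6 |
| 30 | 73.7 | 77.7 | +4.0 | 70.3 | 72.1 | +1.8 |
| 40 | 74.4 | 81.6 | +7.2 | 71.1 | 76.2 | +5.1 |

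At 19 per arm the break-even gap lies between 15 and 20 points.

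**About 30/70 strata**, gaps 0/10/20/30/40: -2.0/-1.1/+1.0/+3.6/+6.3 at 19 per arm; 0/+0.1/+0.4/+1.2/+3.3 at 17.

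**Size of the chi-square at a 25% null, same gaps:** 5.0/4.8/4.4/3.6/2.7% at 19 per arm; 4.5/4.4/4.0/3.3/2.4% at 17. The uncorrected CMH stays between about 4.2% and 5.0%.

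**No blocking within strata** (simulation), gaps 0/20/30/40: -1.9/+0.5/+3.6/+8.2 for N = 38; -2.8/-0.5/+2.4/+7.1 for N = 34. Chi-square size is then 5.0 to 5.2% at every gap, including zero, so the small excess does not come from omitting the stratum.

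**Effect differing by type.** 19 per arm, 20-point gap in controls. If the benefit is about 61 points in the poorer type and 21 in the better, power goes from 73.2% to about 70.7% (-2.5) instead of rising by 1.0. The opposite pattern (about 19 and 59) gives +7.4.

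**Continuity-corrected CMH.** At 19 per arm, equal strata, power is 56.1% at gap 0 (72.9 − 56.1 = 16.8 points below the chi-square) and 68.4% at gap 40 (74.4 − 68.4 = 6.0 below).

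**The case against.** **It is only a preference.** The chi-square is valid, nothing in the protocol contradicts it, and stratum terms are often left to the SAP. What answers this is that the protocol does not leave the test open: it names a univariate chi-square in both places, and that is the only named test that fits closure. What stands is that the gain is modest and conditional. At 17 per arm, the evaluable number planned on, it is under 2 points for gaps up to 30.

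**The gain rests on assumed inputs and can reverse.** This stands in full. The protocol gives neither closure by type nor the mix of types, and it plans to examine whether effects are consistent across types. With 30/70 strata the smaller stratum has only 5 or 6 patients per arm, so the CI for a weighted risk difference is a large-sample approximation there.

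**Stronger readings that the protocol does not support.**
- *The primary test is invalid.* A reader might infer this from the mismatch between design and analysis. The size calculations show the opposite: the test is conservative when type matters and the arms are balanced.
- *The missing stratum explains power below 80%.* The two-sided chi-square reaches only about 69 to 73% even when type has no effect at all. That shortfall comes from the sample-size calculation and is a separate matter.
- *The BCVA analysis has the same fault.* The protocol already defines the outcome as change ("The change of BCVA relative to baseline and the difference between groups from baseline to the 6th month") and states: "The repeated measurement data are analyzed by mixed effect model". All that is left is unstated model terms, which is ordinary SAP detail.

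**Conclusion.** The point holds as an inexpensive, optional improvement to the primary analysis. The design uses detachment type and the named closure test does not. The result is a valid test that loses some efficiency if type is prognostic and the arms are balanced within strata.

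For balanced, equal strata, a two-sided 5% level and the same gap in both arms, the uncorrected CMH changes power by about -2 to +7 points at 19 per arm and 0 to +5 at 17, for gaps of 0 to 40 points. Nothing in the protocol says where in that range the trial lies. A weakly prognostic type, or an effect that differs by type, can make the change negative.

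**What to change.** In section 14 (1) and in the detailed Data analysis section, name the primary closure test as a two-sided 5% Cochran-Mantel-Haenszel test stratified by detachment type as used at randomisation, explicitly without continuity correction. Report a stratum-weighted risk difference with a 95% CI. Keep the plain chi-square as a sensitivity analysis. Fix the choice before outcome data are seen.

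The cost is wording only. Detachment extent must be known before randomisation and is recorded on the baseline slit lamp form (Attachment 1), where the two categories beyond the arcade combine into type 2. Two downsides should be named. If type is not prognostic, about 2 to 3 points of power can be lost (about none at 17 per arm with balanced strata). If software applies the continuity correction by default, the loss at 19 per arm is about 6 to 17 points, more than the largest gain shown here, so the uncorrected form has to be written into the text.

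### The protocol sets out to determine whether effects are consistent across subgroups, but its stated method, separate within-subgroup estimates with 95% CIs, never estimates the difference between subgroup effects

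*Protocol*

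**What the plan says.** The same subgroup paragraph appears twice: in the Summary, section 14 (Statistical data processing), item (3), and in the Specific Study Protocol under Data analysis, item (3).

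- **Aim:** "To determine whether the therapeutic effects of different subgroups are consistent".
- **Method:** outcomes with 95% confidence intervals "are estimated for the major endpoints within the subgroup of the following categorical variables". The variables are detachment type (type 1 within the arcade, type 2 beyond it) and gender.
- **Not stated:** a between-subgroup contrast, a rule for reading the intervals, and the expected subgroup sizes.

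Detachment type is also the stratification factor for randomization (Summary, section 12).

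The sample size text (Summary, section 11) plans on closure rates of 25% in group 1 and 65% in group 2. It adds: "The significant level α is 0.05, and test performance (1- beta) is 0.80". This gives 17 patients per group, raised to 38 in total for 10% loss.

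**The concern.** The aim is inferential: to decide whether the effect is the same in two subgroups. That is a statement about one quantity, the effect in subgroup A minus the effect in subgroup B. The stated method produces two other quantities, each with its own interval, and stops there.

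With 38 patients, each subgroup interval is wide, and whether it excludes zero is close to a coin toss even when the effect is exactly as planned. A reader who looks for the subgroup in which the interval excludes zero will often find one that does and one that does not, by chance alone. At stake is a report that the inverted-membrane procedure works in one detachment type or one sex and not in the other, when the data show no such difference. Such a report could influence which patients are offered the procedure.

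**Working it through.** **1. Inputs.** From the protocol: closure 25% vs 65%, 17 evaluable and 19 randomized per group, two levels per subgroup factor, 95% CIs. Assumed, because the protocol does not give them: the split of each arm between the two subgroups, and that the quantity estimated in each subgroup is the difference in closure rates (the protocol's wording for it is loose).

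**2. The plan's own figure.** With v = 0.25×0.75 + 0.65×0.35 = 0.1875 + 0.2275 = 0.415, the unpooled formula at one-sided α = 0.05 and 80% power gives

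n = (1.645 + 0.842)² × 0.415 / 0.40² ≈ 16.04, rounded up to 17 per group.

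Then 17/0.90 = 18.9, rounded up to 19 per group, 38 in total. The figure reproduces on a one-sided α; the two-sided version of this formula gives 21 per group. The protocol does not state sidedness. That is a separate matter and does not affect what follows.

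**3. Chance that one subgroup's CI excludes zero.** For m patients per arm in a subgroup, sum the binomial probabilities Bin(a; m, 0.25) × Bin(b; m, 0.65) over all pairs (a, b) for which the 95% CI for the difference excludes zero (for Fisher, for which the test is significant at 5%).

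| m per arm | Newcombe | Wald |
|---|---|---|
| 10 | 0.420 | 0.547 |
| 9 | 0.402 | 0.538 |
| 13 | 0.63 | 0.63 |
| 6 | 0.30 | 0.49 |

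**4. Chance that exactly one of the two CIs excludes zero, with identical true effects.** The formula is pA(1 − pB) + pB(1 − pA).

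- 10/9, Newcombe: 0.420×0.598 + 0.402×0.580 = 0.484
- 10/9, Wald: 0.547×0.462 + 0.538×0.453 = 0.496
- 13/6: 0.55 (Newcombe), 0.50 (Wald)
- 14/5: 0.53–0.54
- 9/8 (17 evaluable per arm): 0.49–0.50
- Fisher's exact test: about 0.38 at 10/9, about 0.47 at 13/6

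The result is stable because 2p(1 − p) is flat near its maximum: for equal subgroups with p anywhere from 0.35 to 0.65 it lies between 0.455 and 0.50.

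**5. Other ways to read the same intervals.** Simulation (400,000 runs, Newcombe intervals, identical true effects, splits 9/8, 10/9, 13/6 and 12/5 per arm):

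| Reading taken as inconsistency | Frequency |
|---|---|
| The two CIs do not overlap | about 0.6% |
| The estimates have opposite signs | about 4–5% |
| One estimate lies outside the other's CI | about 28–34% |
| Exactly one CI excludes zero | about 48–55% |

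**6. The direct contrast.** Let Δ be the difference in closure rates in A minus the difference in B, with SE(Δ) = √(v/mA + v/mB).

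- *False signals with identical effects* (simulated, adjusted Wald interval): 3.3% at 10/9, 3.4% at 13/6, 3.1% at 14/5. On the log-odds-ratio scale the rate is 2.2–2.7% over the splits in step 5.
- *Precision:* at 9.5 per arm per subgroup, SE = √(2×0.415/9.5) = 0.296 and the half-width is 1.96×0.296 = 0.58. At 8.5 it is 1.96×0.312 = 0.61. The adjusted Wald interval at 10/9 averages about 0.52. At 14/5, √(0.415/14 + 0.415/5) = 0.336, and the half-width is 0.66.
- *Power* for an effect of 40 points in one subgroup and none in the other: Φ(0.40/0.296 − 1.96) = 0.27 at 9.5 per arm, 0.25 at 8.5, and Φ(0.40/0.336 − 1.96) = 0.22 at 14/5.

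**The case against.** The strongest reply has four parts.

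**No reading rule is stated.** A reader might infer that the planned analysis would show inconsistency in about half of trials. The protocol does not support that. It never says that one CI excluding zero and the other including it counts as inconsistency, and it does not mention significance within a subgroup. The figure of about half describes one possible misreading; under non-overlap the rate is under 1%. This part stands, and it limits the claim.

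**An interaction test may be in the statistical analysis plan.** That plan is not at hand, so the absence of such a test from the protocol is not in itself a defect. This also stands. The point here is narrower: the protocol is not silent but names a method and ties a consistency conclusion to it, and that method does not address the question.

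**The contrast is weak.** With 22–27% power even for 40 points against none, a low false-signal rate is unsurprising, and neither approach can settle consistency with 38 patients. This is correct. But the contrast shows its imprecision in one wide interval, whereas two separate intervals can hide it behind an apparent difference.

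**The stakes are limited and the splits assumed.** The subgroup analysis is secondary, and the primary comparison is untouched. The protocol plans no claim that the surgery works in one subgroup only. Stratified randomization balances the arms within each detachment type but does not make the two types equally common. All of this stands. It affects the weight of the point, not the mismatch between aim and method.

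**Conclusion.** The point holds in a limited form. The stated aim is to determine consistency; the stated method yields two separate estimates and never the difference between them. How often the results would look inconsistent under identical effects runs from under 1% to about 55%, depending on a reading rule that the protocol does not fix. The upper end (48–55%, or about 38% with Fisher's test at a near-even split) applies only if the intervals are read by whether each excludes zero. It rests on the planning rates holding in both subgroups and on assumed splits of 10/9 to 14/5 per arm. The consequence is confined to a secondary analysis; the primary analysis and the sample size are not affected.

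**What to change.** In both places where the subgroup paragraph appears:

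1. Keep the within-subgroup estimates with 95% CIs as a description.
2. Assess consistency by the treatment-by-subgroup contrast, that is, the difference between the two subgroup risk differences with its 95% CI, once for detachment type and once for gender.
3. State that one CI excluding zero while the other does not is not evidence of inconsistency.
4. Label the analysis exploratory and replace *determine* with *explore*.

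The cost is one extra estimate per factor, with no new data, patients or visits. The downside is the imprecision shown above: near an even split the interval is about ±52 to ±61 points, and wider if the split is uneven. The report should say plainly that a trial of this size can neither establish consistency nor rule it out.
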